8.0 Study Endpoints

8.1 Describe the primary and secondary study endpoints.

Response:

The endpoints of this study are:

Primary Efficacy Endpoint:

• Comparison between lamotrigine and placebo groups of the reduction of Ménière's vertigo attacks from baseline

Secondary Efficacy Endpoints:

- Comparison between lamotrigine and placebo groups of vertigo attacks:
- Responder rate: Percentage of patients with > 50% reduction in vertigo attack frequency during treatment vs. baseline
- Vertigo attack free rate analysis: Length of vertigo attackfree intervals, number and percentage of vertigo attack-free days per 28 days period, number and percentage of patients who are vertigo attack-free during the double blind phase
- Comparison between lamotrigine and placebo groups of hearing loss:
- Analysis of audiograms between baseline and end of the study
- Comparison between lamotrigine and placebo groups of symptom severity:
- Ménière's Disease Patients-Oriented Severity Index (MDPOSI)
- Tinnitus Handicap Inventory (THI) questionnaire
- Clinical Global Impression-Severity & Change
- Comparison between lamotrigine and placebo groups of quality of life:
- Dizziness Handicap Inventory (DHI) questionnaire
- AAO-HNS Ménière's disease self-assessment

- Patient Health Questionnaire-9 (PHQ-9)
- Generalized Anxiety Disorder 7-item scale (GAD-7)

8.2 Describe any primary or secondary safety endpoints.

Response:

N/A – no such endpoints

9.0 **Procedures Involved**

9.1 Describe and explain the study design.

Response:

This is a randomized double-blind pilot proof-of-concept clinical trial. The principal investigator and all staff involved in clinic visits will remain blinded until the blind is scheduled to be broken or there is an emergency.

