Participants who are diagnosed with Ménière's disease, as determined by clinical history, ENT confirmation and an audiogram, will qualify if they also have had two or more Ménière's vertigo attacks in a four-week span for two consecutive four-week periods (the qualification period). Those who meet these criteria will then need two or more Ménière's vertigo attacks during a four-week lead-in period to further establish a baseline and verify randomization eligibility. Participants are allowed from the beginning of the lead-in to take their choice of a symptomatic abortive medication according to its package instructions for Ménière's vertigo attacks that last longer than 30 minutes with nausea and/or vomiting. Symptomatic abortive medications include, but are not limited to, meclizine (Antivert), Valium, diazepam, or Zofran. The abortive medication can be used throughout the study regardless of treatment assignment and its use will be recorded. Twelve eligible participants, with a minimum total of six attacks during the qualification and lead-in periods, will be randomly assigned to either a placebo or lamotrigine treatment group. Randomization will be conducted by UBSoPPS Research Pharmacy. The study drug and matching placebo will be titrated from 25mg twice a day (BID) up to 150mg BID over a six week period. During titration, clinic visits are scheduled every two weeks to assess any adverse events, symptoms, quality of life, and compliance. Those who cannot tolerate the 150mg BID dose may return to a 100mg BID dose during an unplanned visit. However, if a participant is unable to tolerate the 100mg BID dose they will be withdrawn from the study. Participants will maintain the 150mg BID or 100mg BID dose for a 12-week period with clinic visits every four weeks to assess their progress. Between all study visits, participants are asked to complete a daily survey describing their symptoms. This survey is hosted by polleverywhere.com and can be completed through text message, an online website, or with a paper document- whatever method is preferred by the participant. At the conclusion of the 12-week study period, a study staff will be un-blinded

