and will give participants assigned to the lamotrigine group the option to continue the study medication as a long-term open-label use outside of the study or to begin a two-week taper off. The number of participants who decide to continue the study medication will be noted, but the participant will be terminated from the study and thus responsible for all following costs. Those assigned to the placebo treatment will be informed of their treatment assignment and terminated from the study.

9.2 Provide a description of all research procedures being performed and when they are performed, including procedures being performed to monitor subjects for safety or minimize risks.

Response:

Please note: these procedures are a continuation from section 3.2, where section 3.2 outlines the screening procedures that are also part of standard medical care, and this section, section 9.2, is specific to research-only procedures.

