Four weeks later participants return to the clinic for Visit 8, current medications and adverse events will be reviewed by the Principal Investigator. The Principal Investigator will also administer a neurological and physical exam and complete the Clinical Global Impression-Severity and Change assessment. A staff member will collect medication containers, conduct a pill count and collect and review the dosage log and daily Ménière's survey responses. Participants will complete the questionnaire batch, and undergo a comprehensive audiogram with tympanometry. Blood will be drawn, centrifuged and shipped to Kaleida Health's labs to analyze study drug levels, CMP, CBC, and a urine pregnancy test will be conducted for female participants of reproductive age (<50yrs). Additionally, a urine sample will be obtained for 24 hour creatinine clearance analysis as a screening measure for healthy kidney and liver function. At the conclusion of the visit a staff member will be un-blinded by unsealing an envelope that contains treatment code and participant number. Those in the lamotrigine group will be given the option to be terminated from the study, but to continue the study medication at their own cost. Alternatively, they can continue in the study and begin to taper off the study drug. Those who decide to continue the study medication will be noted, but no further study participation is required. Participants continuing lamotrigine will be free to follow up on their treatment through the Dizziness and Balance Clinic or through a physician of their choice. Participants who decide to discontinue the study drug will begin a two-week taper consisting of one week at their current dosage QD and then one week of half the current dosage QD, and be paid for these 2 remaining study visits 9 and 10. Those assigned to the placebo group will be terminated from the study and are informed that they are allowed to seek treatment for their Ménière's disease at the Dizziness and Balance Clinic or elsewhere.

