The drug supply will be sent to the University of Buffalo's School of Pharmacy and Pharmaceutical Sciences (UBSoPPS) Research Pharmacy. Once it arrives the packing slip will be checked for completeness and then the study staff will be notified of its arrival. The invoice and inventory taken will be faxed over to the study site. The drugs will then be stored in their original containers in a room-temperature, dry and dark area of the UBSoPPS Research Pharmacy's lab, which has very limited access since it is a pharmacy. Temperature and humidity will be monitored by a UBSoPPS Research Pharmacist.

UBSoPPS Research Pharmacy will take the manufacture supplied tablet and place it inside a capsule. The capsule will be filled with methylcellulose until the entire content of the capsule is filled, decreasing the chance for un-blinding, and the capsule then closed. The encapsulated lamotrigine will then be packaged in an amber vial with a study label. Repackaging will follow NYS regulation. Repacking will be conducted by a pharmacist or under his/her immediate and personal supervision. A repacking record shall be maintained for five years, including the name, strength, lot number, quantity and name of the manufacturer and/or distributor of the drug repacked, the date of repacking, the number of packages prepared, the number of dosage units in each package, the signature of the person performing the repacking operation, the signature of the pharmacist who supervised the repacking, and such other identifying marks added by the pharmacy for internal recordkeeping purposes. Drugs repacked shall have an expiration date 12 months, or 50 percent of the time remaining to the manufacturer's expiration date, whichever is less, from the date of repacking.

SUNY at Buffalo School of Pharmacy and Pharmaceutical Sciences (UBSoPPS) Research Pharmacy will randomize eligible participants through www.randomizer.org. An UBSoPPS pharmacist will generate 12 random sets of numbers, ranging from 1-2 for the two assignment groups, with one unique number per set. UBSoPPS Research Pharmacy will use this randomization to compile a master log with the participant number and treatment code.

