Response: According to our preliminary data, the mean number of vertigo attacks after 3 months of treatment with Lamotrigine was 4.91 (SD=7.24), and we expect the mean number of vertigo attacks in the placebo group to be approximately 13. We assumed Negative Binomial distribution for the response, two-sided tests, level of significance 0.05 and considered various sample sizes, mean and variance of the number of attacks in the two groups. We calculated the associated power for comparison of the mean response between the two groups by utilizing Monte Carlo simulations and using Negative Binomial regression model with log link. Each simulation consisted of 1000 iterations and was conducted in R (http://www.r-project.org/). This analysis showed that a power above 80% can be obtained with a sample of 12 participants.

Table: Associated Power for Comparison of the Mean Response between Treatment Groups Calculated with Monte Carlo Simulations and Negative Binomial Regression Model with Log Link

Total N	Mean Number	Standard	Mean Number	α	Power
	of Attacks in	Deviation of	of Attacks in	level	
	Lamotrigine	the number of	Placebo group		
	group at the end	attacks	at the end of		
	of the study		the study		
12	5	7.24	13	0.05	57.6
12	5	6	13	0.05	60.6
12	5	4	13	0.05	86.6
12	6	6	13	0.05	58.2
12	6	4	13	0.05	83.5
14	5	7.24	13	0.05	60.7
14	5	6	13	0.05	70.1
14	5	4	13	0.05	92.8
20	5	7.24	13	0.05	67.6
20	5	4	13	0.05	97.6
20	5	7.24	12	0.05	60.4
20	5	4	12	0.05	94.5
20	6	7.24	12	0.05	48.8
20	6	4	12	0.05	91.9
34	5	7.24	13	0.05	82.2
34	5	6	13	0.05	92.5

Update on 6/4/2015:

As of 6/4/2015		
Expected N complete		
Complete		
Currently enrolled		
Potentially eligible, not enrolled		
Screened & eligible but declined participation in study		
Screened and ineligible		
Started study but dropped out		
TOTAL		

We engage in a multi-step process to reduce drop-outs, however, this is a very long study (6 months), and some drop-outs are to be expected. Thus far, we've had 2 participants drop out of the study and 8 have completed. Therefore, our dropout rate is 25%. To compensate for drop-outs, we request to increase our enrollment by 25%, rounded to the nearest whole number attain equal numbers in each group, for a total N of 16.

11.3 Describe the steps that will be taken secure the data (e.g., training, authorization of access, password protection, encryption, physical controls, certificates of confidentiality, and separation of identifiers and data) during storage, use, and transmission.

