This is a small (n=12), single location pilot study on the use of Lamotrigine to treat Meniere's disease. The study employs procedures that do not provide sufficient information to conduct statistical testing for potential harm. The main reason for this is because the way in which harm is determined is through probing participants about any side effects, adverse events, or complains at every study visit, as well as providing them with a means of contacting us M-F 8am-4:30pm if they experience any side effects between study visits. Additionally, the consent form outlines specific side effects to watch for that can be associated with the drug, including the course of medical action they should take if they develop the most common allergic reaction (rash). Finally, participants are explicitly asked at the time of consent whether or not they agree to report all adverse effects to the PI or research staff throughout the duration of the study, regardless of whether they believe it is related to the drug or not. All participants must agree to this in order to be in the study. While we have not encountered any adverse events or side effects, if we did, the PI would be informed and we would complete an adverse event report and submit to IRB immediately.

12.8 Describe any conditions that trigger an immediate suspension of the research.

Response: The research will be immediately suspended if the study drug is found to be unsafe due to a drug recall or similar event, or if the safety, security, or functionality of the facilities at which the study takes place become compromised in any way.

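### Does a randomisation list written for 12 leave participants 13 to 16 without a valid allocation, and do simple draws matter?

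*Combined protocol and SAP*

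**What the plan says.** The allocation text is the same in 9.4 and 30.1. The research pharmacy randomises eligible participants with an online generator, and the pharmacist will "generate 12 random sets of numbers, ranging from 1-2 for the two assignment groups, with one unique number per set". The result becomes a master log of participant number and treatment code. No blocks, strata or balancing rule are mentioned. Sections 3.2 and 9.2 add that assignment follows a randomisation carried out by the pharmacists and give no upper limit on numbers.

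Section 9.1 sets the scale: "This is a randomized double-blind pilot proof-of-concept clinical trial", and "Twelve eligible participants, with a minimum total of six attacks during the qualification and lead-in periods, will be randomly assigned". Section 12.7 agrees: "This is a small (n=12), single location pilot study on the use of Lamotrigine". Section 23.1 also gives 12 as the accrual. Section 23.2 uses 12 as the number needed to complete, with 2 to 5 drop-outs expected.

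The update of 6/4/2015 in 11.2 reports "2 participants drop out of the study and 8 have completed". It then requests an increase in enrolment, "rounded to the nearest whole number attain equal numbers in each group, for a total N of 16".

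Codes are opened as each participant finishes. At Visit 8 (section 9.2): "At the conclusion of the visit a staff member will be un-blinded by unsealing an envelope that contains treatment code and participant number". Section 9.1 adds: "Those assigned to the placebo treatment will be informed of their treatment assignment and terminated from the study".

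**The concern.** Two things look wrong. First, a 12-code list cannot serve 16 people. A quarter of the enlarged sample (4/16) appears to have no written allocation procedure, so a reader might wonder whether those codes were drawn afresh or chosen to even up the arms. Secondly, the update speaks of equal groups, while independent draws seldom deliver them.

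If late codes had been picked to force balance, staff who had seen earlier codes opened could infer the later ones, and allocation concealment would suffer. If the arms came out badly unequal, a trial with little power to spare would lose some of it.

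**Working it through.** **The figure of 16.** Multiplying, 12 × 1.25 = 15, which rounds up to 16 for an even total. Dividing by the completion fraction, 12/(1 − 0.25) = 16. The drop-out rate is given as 25%, but 2 out of 10 is 20%. At 20%, 12/0.80 = 15, which again becomes 16 once the total must be even. The figure of 16 stands either way. The equal-groups phrase explains the step from 15 to 16. It is not a promise that the randomised numbers will match exactly.

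**What the draw is.** Each set holds one number and there are only two possible values, so uniqueness within a set cannot restrict anything across 12 sets. The scheme is independent 1:1 draws.

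**How often the arms are unequal.** With Binomial(n, 0.5):

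- N = 12, exact 6:6: 924/4096 = 22.6%
- N = 16, exact 8:8: 12870/65536 = 19.6%
- N = 16, 5:11 or worse: 2 × (1 + 16 + 120 + 560 + 1820 + 4368)/65536 = 13770/65536 = 21.0%
- N = 16, 4:12 or worse: 5034/65536 = 7.7%

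**What imbalance costs.** The inputs are the means of 5 and 13 and the SD of 7.24 from the table in 11.2. The table gives one SD, and it is assumed here for both arms. Counts are negative binomial, and the test is an exact two-sided rank-sum at 0.05, found by simulation with N = 16:

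| On drug : placebo | Power | Difference from 8:8 |
|---|---|---|
| 8:8 | 69.9% | – |
| 5:11 | 61.6% | −8.3 points |
| 11:5 | 64.2% | −5.7 points |
| Average over simple draws | 66.6% | −3.3 points |

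At SD 6 the 8:8 and average figures are 76.6% and 73.3%. At SD 4 they are 93.7% and 91.5%, a loss of 2.2 points.

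These powers are for end-of-study counts, whereas 11.1 compares reductions from baseline. They also come from a different test than the regression behind the 11.2 table, so only the differences between splits should be read from them.

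**What blocking could recover.** At least 10 codes had been used by the update (8 completed + 2 dropped out, taking both drop-outs as randomised), so at most 16 − 10 = 6 remained. The number then enrolled cannot be read from the table in 11.2, so the range is shown. Earlier codes are simple draws, later ones come from blocks of 2 and 4 in random order, and SD is 7.24:

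| Codes blocked | Exact 8:8 | 5:11 or worse | Average power | Gain |
|---|---|---|---|---|
| 0 | 19.6% | 21.0% | 66.6% | – |
| 2 | 20.4% | 18.9% | 66.9% | 0.3 |
| 4 | 22.4% | 15.2% | 67.4% | 0.8 |
| 6 | 24.0% | 11.8% | 67.8% | 1.2 |

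Exact balance stays at about one time in four or five whatever is done with the remaining codes.

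**The case for a change.** The strongest case for a change is that allocation underlies the whole comparison and a written scheme should cover everyone randomised. One sentence would settle how the last four codes arise, and concealed blocks of varying size would narrow the chance of a 5:11 split from 21.0% to between 11.8% and 18.9%, at almost no cost.

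Part of this stands. The list length in 9.4 and 30.1 was not brought into line with 11.2, and 9.1 and 23.1 also still say 12. That is a real inconsistency.

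The rest carries less weight. The pharmacy, the generator and the two-value draw are stated without a ceiling, so the natural continuation is four more draws of the same kind. Nothing in the plan suggests that balance would be forced. The update is worded as a request, its approval is not shown, and the pharmacy log is not part of the documents and may already run to 16. Section 12.7 rests on a discussion dated 3/20/2015, before the update. Section 23.2, with 12 completers and 2 to 5 drop-outs, already implies 14 to 17 entrants.

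Simple draws also have a merit here. Since codes are opened person by person at Visit 8, independence means that knowing past codes says nothing about the next one. Blocks give up a little of that.

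**Conclusion.** No change follows. The number 12 in the randomisation text is a clerical carry-over, and the pharmacist can fill the gap in the obvious way. Simple 1:1 randomisation is valid at any list length. The rank-sum test, Fisher's exact test and the mixed model in 11.1 all accept unequal arms, and the baseline comparison by group planned there will show the split achieved.

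The average cost against a fixed 8:8 split is 2.2 to 3.3 points of power over SDs of 4 to 7.24. Blocking what was left could return at most about 1.2 points at SD 7.24, and nothing if all codes had been issued. Equal randomised numbers would not secure equal analysed numbers either, because drop-outs are expected and section 13.3 stops data collection at withdrawal.

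The conclusion assumes that codes 13 to 16 come from the same pharmacy draw and are not chosen to reach a target split. The power figures further assume a common SD in both arms, 16 participants analysed and end-of-study counts. Different assumptions would move the levels, but the validity of the allocation does not depend on them.

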10.0 Data and Specimen Banking

10.1 If data or specimens will be banked for future use, describe where the data/specimens will be stored, how long they will be stored, how the data/specimens will be accessed, and who will have access to the data/specimens.

Response: Blood samples will be collected, centrifuged and packed before being shipped for analysis in the Dent Neurologic Institute Infusion Clinic located within the Dent Neurologic Institute. Kaleida Health Laboratory is located only a four-minute drive away from Dent Neurologic, making the shipping and processing of blood samples simple and easy. All biologic products will be disposed of properly as biologically hazardous waste after the described testing is complete, so there will be no storage of materials for further use.

10.2 List the data to be stored or associated with each specimen.

Response: There will be no storage of materials for further use.

10.3 Describe the procedures to release data or specimens, including: the process to request a release, approvals required for release, who can obtain data or specimens, and the data to be provided with specimens.

Response: N/A

11.0 Data Management

11.1 Describe the data analysis plan, including any statistical procedures.

Response: The primary response will be the number of vertigo attacks as measured at baseline and at the end of the study period. The secondary responses will include the percentage of vertigo free patients, audiograms, symptom severity scales and quality of life scales (listed in the Approach section). The analysis set will include all subjects who are randomized and receive at least one dose of the study medication or the placebo. Integer or continuous variables will be presented by their mean and median and their SD and IQR. Categorical variables will be summarized using counts and percentages. Demographic and baseline characteristics of the enrolled subjects will be summarized through descriptive statistics for continuous variables and through frequencies for categorical variables. Demographic and baseline characteristics of the intervention and placebo groups will be compared to assess for comparability. Continuous variables will be compared using Wilcoxon rank-sum test and categorical variables will be compared through Fisher's exact test. We will test for reduction in the Ménière's vertigo attacks from baseline through Wilcoxon's sign rank test and will compare the reduction between the two treatment groups using Wilcoxon rank-sum test. The tests will be two-tailed and the significance level will be set to 0.05. Additionally, we will perform statistical modeling of the number of vertigo attacks longitudinally through generalized linear mixed effects model using Poisson or Negative Binomial distribution as appropriate. Data analysis will be conducted using SAS (SAS Institute Inc., Cary, NC, USA) and R (http://www.r-project.org/). All data analyses will be performed by [name] of the SUNY UB Statistical Consultant Laboratory.

11.2 Provide a power analysis.

Response: According to our preliminary data, the mean number of vertigo attacks after 3 months of treatment with Lamotrigine was 4.91 (SD=7.24), and we expect the mean number of vertigo attacks in the placebo group to be approximately 13. We assumed Negative Binomial distribution for the response, two-sided tests, level of significance 0.05 and considered various sample sizes, mean and variance of the number of attacks in the two groups. We calculated the associated power for comparison of the mean response between the two groups by utilizing Monte Carlo simulations and using Negative Binomial regression model with log link. Each simulation consisted of 1000 iterations and was conducted in R (http://www.r-project.org/). This analysis showed that a power above 80% can be obtained with a sample of 12 participants.

Table: Associated Power for Comparison of the Mean Response between Treatment Groups Calculated with Monte Carlo Simulations and Negative Binomial Regression Model with Log Link

Total N	Mean Number	Standard	Mean Number	α	Power
	of Attacks in	Deviation of	of Attacks in	level	
	Lamotrigine	the number of	Placebo group		
	group at the end	attacks	at the end of		
	of the study		the study		
12	5	7.24	13	0.05	57.6
12	5	6	13	0.05	60.6
12	5	4	13	0.05	86.6
12	6	6	13	0.05	58.2
12	6	4	13	0.05	83.5
14	5	7.24	13	0.05	60.7
14	5	6	13	0.05	70.1
14	5	4	13	0.05	92.8
20	5	7.24	13	0.05	67.6
20	5	4	13	0.05	97.6
20	5	7.24	12	0.05	60.4
20	5	4	12	0.05	94.5
20	6	7.24	12	0.05	48.8
20	6	4	12	0.05	91.9
34	5	7.24	13	0.05	82.2
34	5	6	13	0.05	92.5

Update on 6/4/2015:

As of 6/4/2015		
Expected N complete		
Complete		
Currently enrolled		
Potentially eligible, not enrolled		
Screened & eligible but declined participation in study		
Screened and ineligible		
Started study but dropped out		
TOTAL		

We engage in a multi-step process to reduce drop-outs, however, this is a very long study (6 months), and some drop-outs are to be expected. Thus far, we've had 2 participants drop out of the study and 8 have completed. Therefore, our dropout rate is 25%. To compensate for drop-outs, we request to increase our enrollment by 25%, rounded to the nearest whole number attain equal numbers in each group, for a total N of 16.

11.3 Describe the steps that will be taken secure the data (e.g., training, authorization of access, password protection, encryption, physical controls, certificates of confidentiality, and separation of identifiers and data) during storage, use, and transmission.

Response: Data will be password protected and participant identity will be coded to ensure confidentiality of information. The participant code number and identifying information will be kept in a locked office in the Dent Neurologic Institute and the UBSoPPS Research Pharmacy. At the conclusion of the study only the PI, Co-Investigator, Statistician, or Research Assistant at Dent Neurologic Institute will have access to the data and participant information.

11.4 Describe any procedures that will be used for quality control of collected data.

Response: The data will be accurately entered twice in a password protected Excel Spreadsheet and checked automatically by an Excel program for accuracy. Data will only be viewed and analyzed by the research personnel.

11.5 Describe how data and specimens will be handled study-wide:

Response: Please see 11.3 and 11.4

- 11.6 What information will be included in that data or associated with the specimens?
 - Response: Ménière's Disease Patients-Oriented Severity Index (MDPOSI)
 - □ Tinnitus Handicap Inventory (THI) questionnaire
 - □ Clinical Global Impression-Severity & Change
 - Dizziness Handicap Inventory (DHI) questionnaire
 - □ AAO-HNS Ménière's disease self-assessment
 - □ Patient Health Questionnaire-9 (PHQ-9)
 - □ Generalized Anxiety Disorder 7-item scale (GAD-7)
 - \Box Dosing Log
 - □ Meniere's daily survey
 - □ Pertinent results of neurological or physical exams
 - \Box Drug dosing
 - \Box CBC, CMP blood tests
 - □ Lamotrigine blood levels

□ De-identified demographics information

